3. OBJECTIVES AND PURPOSES OF THE TRIAL

For newborn infants born with a deficiency in lung surfactant because of prematurity or other causes of delayed lung maturation lung surfactant replacement therapy is life saving.^{2,3,4} The objective of this trial is to demonstrate that there is a group of patients who can benefit from surfactant replacement therapy with lower risk of administration complications and less discomfort by utilizing an alternative, safer administration technique – aerosolization.

Currently surfactant replacement therapy requires instillation of a liquid suspension into the airways. In order to instill into the airways it is necessary that an endotracheal tube be inserted and the surfactant administered through the endotracheal tube. A single dose may not be sufficient therapy and, if repeat dosing is likely or inevitable, a decision has to be made to either prolong the time of intubation or to remove the tube and possibly subject the patient to re-

intubation. One purpose of this trial is to determine if aerosolizing Infasurf provides an effective alternative for some patients that enable delivery of surfactant replacement therapy without subjecting them to the pain, discomfort and risk of endotracheal intubation or re-intubation.

The volume of the liquid instillation of the currently approved surfactants (2.5 to 4.0 mL/kg body weight) is larger than the total volume of the airways below the trachea which is 1 ml/kg body weight. Complications at administration are the physiologic consequences of two processes: (a) liquid obstruction of some airways, and (b) stimulation of irritant receptors in the lung. Liquid obstruction can produce transient low blood oxygen and high blood carbon dioxide, which together with neurally mediated irritant reflexes result in transient cardiopulmonary dysfunctions: cyanosis, tachycardia, bradycardia, hypotension, hypertension, airway obstruction and reflux of surfactant. Aerosolized delivery has the potential of minimizing both airway obstruction by liquid and the stimulation of irritant receptors in the lung.

Specifically the Objectives of the Trial are:

- (a) Document superiority of aerosolized of Infasurf to usual care in early RDS in preventing the need to intubate and instill a liquid surfactant suspension into the patient.
- (b) Show acute improvement in respiratory function by aerosolized Infasurf.
- (c) Document that aerosolized Infasurf is as safe as “usual care” for RDS patients.

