5. SELECTION AND WITHDRAWAL OF SUBJECTS

5.1 Inclusion criteria

Cohort 1: RDS Patients Who Did Not Have Early Surfactant Instillation

- 1) NICU patient, ≥ 1 hour of age and < 12 hours of age.
- 2) Clinical diagnosis of RDS, with or without chest X-ray data.
- 3) Inspired oxygen $\geq 25\%$ and $\leq 40\%$ to maintain adequate oxygen saturation.
- 4) Not intubated
- 5) Requiring:
 - (a) nasal continuous positive airway pressure (nCPAP), or
 - (b) high flow nasal cannula (≥ 2 L/kg/min) (HFNC), or
 - (c) non-invasive ventilation.

Cohort 2: RDS Patients Post Early Surfactant Instillation

- 1) NICU patient <24 hours of age.
- 2) Intubated, given instilled surfactant at \leq 1hours of age, then extubated within 6 hours.
- 3) Inspired oxygen \geq 25 and \leq 40 % to maintain adequate oxygen saturation.
- 4) Not intubated.
- 5) Requiring: (a) nasal continuous positive airway pressure (nCPAP),or
(b) high flow nasal cannula (\geq 2 L/kg/min) (HFNC), or
(c) non-invasive ventilation.
- 6) Increasing in FiO₂ and/or respiratory support for \geq 1 hour.

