7.2 Efficacy methods

All data will be extracted from each patient's medical record and entered into a case report form. No specific testing is defined. Data to be extracted to assess efficacy is:

- 1) Requirement for Instilled Surfactant to 72 hours of age.

- Number of patients requiring surfactant instillation from randomization to 72 hours of age. Intubation and instillation is indicated if there is a continuing, > 1hour, requirement for >40% inspired oxygen plus continuing positive pressure support to maintain acceptable blood oxygen saturations.

2) Measures of Severity of RDS from Randomization to Surfactant Instillation or 72 hours of age.

- (a) Supplemental oxygen measured as the increase and/or decrease over time.
- (b) Duration of positive pressure respiratory support over time.

3) Duration of RDS to 7 days of age :

- (a) Time from birth to when patient last required >25% oxygen.
- (b) Requiring >25% oxygen for ≥7 days (168 hours) from birth shall be defined as “unresolved RDS”.

4) Incidence of pulmonary complications to 7 days of age

- (a) Occurrence(s) of radiologically or clinically diagnosed pneumothorax, pneumomediastinum, pulmonary interstitial emphysema, subcutaneous emphysema or pneumopericardium.
- (b) Pulmonary hemorrhage defined as gross bleeding from the airway, changes in a chest X-ray consistent with pulmonary hemorrhage and acute deterioration of respiratory function.
- (c) Acute pneumonia defined as acute deterioration of respiratory function accompanied by clinical and chest X-ray findings consistent with bacterial pneumonia and a clinical decision to institute appropriate antibiotic therapy for acute pneumonia.

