8. ASSESSMENT OF SAFETY

8.1 Parameters

Adverse Events During Aerosolization.

- 1) Discontinuation of aerosolization before the full dose is given for any reason
- 2) Incidence, magnitude and duration of adverse cardiopulmonary effects:
 - (A) Hypoxemia defined as O₂ saturation of < 80 % for >1 minute despite interventions.
 - (B) Airway obstruction defined as blockage of ventilation for >1 minute producing hypoxemia and bradycardia and requiring endotracheal suctioning and/or re-intubation.
 - (a) during Infasurf aerosolization(s)
 - (b) during instillation(s)
 - (C) Other.

Other safety parameters: These data will be extracted from the medical record of each patient from birth to 28 days of life, death or discharge (whichever is first).

- 1) Incidence of pneumonia, sepsis or other major infection to 28 days
- 2) Incidence and severity of seizures, brain hemorrhages or other brain injuries
- 3) Incidence and severity of necrotizing enterocolitis
- 4) incidence and severity of bronchopulmonary dysplasia.
- 5) Incidence and severity of any other severe unexpected adverse events.

8.2 Methods Identification of all safety outcomes will be by review of the patient’s medical record.

8.3 Analysis Severe, unexpected adverse events. Any severe, unexpected adverse event occurring to aerosolized assigned patients will be immediately reported to the medical director of a participating site. The medical director will review the adverse event and determine if it is related, or possibly related, to the administration of aerosolized Infasurf. If the event is considered “related” or “possibly related” the sponsor will be immediately notified and will be responsible for filing the appropriate notification to FDA. The sponsor will provide the same information to the study chair and to the other study sites. The local site P.I. will be responsible for providing the local IRB with the information about the event.

Non-serious adverse events By regulation an “adverse event means any untoward medical occurrence associated with the use of a drug in humans, whether or not considered drug related.” (21 CFR 312.32(a)).

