Randomization: Subjects will be randomized to the intervention or active control arm in a 1:1 fashion using a stratified permuted block randomization scheme with variable block sizes of 2 and 4. Randomization lists will be generated by the study biostatistician which will then be used to create an envelope-based system to be used at the individual study sites. Subjects will be included in primary data analyses according to their randomized assignment irrespective of the treatment actually received (intent-to-treat). Exceptions would include those who withdraw their consent to use any of their data prior to subject evaluation.

Accrual. Subjects will be accrued to the study on a first-come basis. The projected accrual is approximately 80 per month, and therefore recruitment is expected to be complete at most 365 days following the study starting point. Subjects will be followed to hospital discharge or 28 days whichever is shorter so total study duration will be approximately 13 months.

Descriptive analyses. Measured outcome variables will be summarized overall and by relevant demographic and baseline variables. Descriptive statistics such as frequencies and relative frequencies will be computed for all categorical variables. Numeric variables will be summarized using simple descriptive statistics such as the mean, standard deviation and range. A variety of graphical techniques will also be used to display data, ex. histograms, boxplots, scatterplots, etc.

Primary efficacy analyses. The primary efficacy analysis will be performed within each cohort separately and is based on a test for superiority of the experimental treatment relative to active control with regards to intubation rate. An overall assessment of the probability of intubation differences across study sites will be done using the Cochran-Mantel-Haenszel test. A one-sided nominal significance level of 5% will be utilized. Additional analyses will be performed utilizing both cohorts of subjects in order to assess differential treatment effects.

Primary safety analyses. All adverse events will be recorded during the study period and then tabulated at the end of the study.

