4. Respiratory Status Randomization From Birth to 72 Hours of Age for All Patients
(source respiratory and nursing sheets or charts)

Date	Time	Age (hrs)	FIO ₂	CPAP	HFNC >2/kg/min	Non-invasive ventilation	Mechanical ventilation/oscillation
		6					
		12					
		18					
		24					
		36					
		42					
		48					
		54					
		60					
		66					
		72					

5. Endotracheal Intubations +/- Surfactant Instillation (source procedure note)

# previous intubations	Age (hrs)	FiO ₂	Surfactant (Inf,Curo,Surv)	Surfactant Dose (ml/kg)	Complications of Surfactant Instillation* (all that apply)
0					
1					
2					

* 1=cyanosis; 2=bradycardia, 3=reflux, 4=airway obstruction 5= hypotension 6= re-intubated 7=required CPR

6. Imaging Results Days 1-4 (source report of radiologist interpreting the image(s))

Imaging	Day 1		Day 2		Day 3		Day 4	
	Normal	Abnormal	Normal	Abnormal	Normal	Abnormal	Normal	Abnormal
Chest X-ray(s)								
Head ultrasound(s)								
Other ultrasound(s)								
Other X-ray(s)								
CT scan(s)								
MRI (s)								

[figure not shown]
[figure not shown]
Chest X-Ray abnormality is defined as a diagnosis, not just a description (1)RDS; (2)pneumothorax (3)PIE (4) pneumomediastinum (5) pneumonia (5) interstitial edema (6) pulmonary hemorrhage (7) other

Head ultrasound abnormality (1)IVH grade 1 or 2 (2) IVH grade 3 or 4 (3) PVL (4) HIE (5) cerebral edema (6) other

7. Patient Outcomes on Days 4, 8, and 29 of Life and Discharge Summary
 (source progress notes on days 5, 9, and 29 or discharge (D/C))

Organ System	Diagnoses	Day 4	Day 8	Day 29 or D/C
Status	(1)Alive (2)Deceased (3)Ventilated (4)On CPAP/HFNC/NIV (5)On O ₂ for RDS (6)On O ₂ for apnea (7)Other			
CNS	(1)IVH-1/2 (2)IVH-3/4 (3)HIE (4)PVL (5)Seizures (6)Apnea (7)Cerebral edema (8)Other			
Respiratory	(1)RDS (2)Pneumothorax (3)PIE (4)Pneumonia (5)Pulmonary hemorrhage (6)Pneumomediastinum (7)BPD (7) Other			
Cardiovascular	(1)CHF (2)Hypotension (3)Hypertension (4)PDA (5)PDA Rx drugs (6)PDA Rx surgery (7)Arrhythmia (8)Other			
GI	(1)NEC stage 1 (2)NEC stage 2 (3)NEC stage 3 (4)GI bleeding (5)diarrhea (6) GE reflux (7)other			
Renal	(1)Oliguria/anuria (2)Uremia (3)Hypernatremia (4)Hyponatremia (5)Hyperkalemia (6)Hypokalemia (7)Other			
Metabolic	(1)Hypoglycemia (2)Full parenteral feedings (3)Partial parenteral feedings (4)Full oral feedings (5)Other			
Hematologic	(1)Neutropenia (2)Thrombocytopenia (3)Coagulopathy (4)Other			
Infection	(1)Sepsis (2)Meningitis (3)Cellulitis (4)Other			

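### Safety data run from birth, the instillation item has no start point, and no rule separates events before randomization from those after it

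*Combined protocol and SAP*

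**What the plan says.** Section 8.1 has two blocks. The first, headed "Adverse Events During Aerosolization", includes adverse cardiopulmonary effects arising during aerosolization or "during instillation(s"); it states no time window. The second covers infection, brain injury, necrotizing enterocolitis, bronchopulmonary dysplasia and other severe unexpected events. Data for that block are to be "extracted from the medical record of each patient from birth to 28 days of life, death or discharge", whichever is first.

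The only safety analysis rule is in section 9.1: "All adverse events will be recorded during the study period and then tabulated at the end of the study". The study period is not defined there, and neither section has a baseline or treatment-emergent rule.

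Section 4.5 allows randomization up to 12 hours of age in cohort 1 and 24 hours in cohort 2. Section 5.1 requires every cohort 2 infant to have been intubated and instilled at or before 1 hour of age, "then extubated within 6 hours".

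Case report form item 5, "Endotracheal Intubations +/- Surfactant Instillation (source procedure note"), starts at zero previous intubations and records age in hours and complications on each row. Item 6 records imaging by day. Item 7 records diagnoses at days 4, 8 and 29 or discharge, without onset times.

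The primary endpoint is anchored differently, in section 7.2: "Number of patients requiring surfactant instillation from randomization to 72 hours of age".

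**The concern.** An event before randomization cannot have been caused or prevented by the assigned arm. Randomization makes such events equally frequent in both arms on average. Including them adds the same amount to each side, which moves ratios toward 1.

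That matters in two directions. Objective (c) in section 3 is to document that aerosol is as safe as usual care, so if aerosol does harm, dilution favours the conclusion the trial hopes to reach. Section 3 also claims "lower risk of administration complications and less discomfort", so if aerosol does reduce instillation complications, the same dilution hides part of the benefit.

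**Working it through.** **The plan's own figure.** The documents give no safety rate, margin or power. The nearest figure that can be checked is the efficacy power in section 9.2: 229 per group, 60% vs 48%, one-sided 5%. With a continuity correction:

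Φ{[0.12 − 1/229 − 1.645·√(2×0.54×0.46/229)] / √[(0.60×0.40 + 0.48×0.52)/229]} = Φ{(0.1156 − 0.0766)/0.0462} = Φ(0.844) = 80.1%.

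This matches the plan. It is unaffected by this point, because the primary endpoint starts at randomization. It does confirm how the assumed rates are used, so I take the cohort 2 rates from the same section.

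**Step 1. Which listed harms can precede randomization.**
- Bronchopulmonary dysplasia: no. Section 4.1 assesses it at 28 days or discharge.
- Grade 3/4 intraventricular hemorrhage: excluded at entry, but only if known (section 5.2).
- Acute hypoxic encephalopathy, with or without seizures: excluded at entry (section 5.2).
- Lower-grade hemorrhage, early infection and other severe events: not excluded, so yes.
- Complications of the birth instillation in cohort 2: yes, if the instillation item is read to include it.

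**Step 2. Cohort 2 instillations, if the birth instillation is counted.** Inputs: 200 infants allocated 1:1, hence 100 per arm; 60% vs 42% (section 9.2). Assumptions: one qualifying instillation per infant, and one later instillation for each infant who meets the primary endpoint.

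| | Usual care | Aerosol | Relative reduction | Difference |
|---|---|---|---|---|
| After randomization | 60 | 42 | 1 − 42/60 = 30% | 18 |
| From birth | 100 + 60 = 160 | 100 + 42 = 142 | 1 − 142/160 = 11.25% | 18 |

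Share before treatment: 200/(200 + 102) = 200/302 = 66%. As a proportion of infants with any instillation, 60% vs 42% becomes 100% vs 100%.

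**Step 3. Infants with any instillation complication, cohort 2.** Let q be the complication risk per instillation (assumed; not in the documents), independent between instillations. After randomization the risks are 0.60q and 0.42q, so the ratio is 0.70 for any q. From birth they are 1 − (1 − q)(1 − 0.60q) and 1 − (1 − q)(1 − 0.42q).

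| q | After randomization | From birth | Ratio from birth | Risk difference, points |
|---|---|---|---|---|
| 10% | 6.0% vs 4.2% | 15.4% vs 13.8% | 0.89 | 1.8 → 1.6 |
| 50% | 30.0% vs 21.0% | 65.0% vs 60.5% | 0.93 | 9.0 → 4.5 |

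Over q from 5% to 50% the ratio from birth lies between 0.89 and 0.93.

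**Step 4. Other harms.** Let b be the proportion of infants, equal in both arms, with the event before randomization. The any-event risk from birth is b + (1 − b)p, so the risk difference shrinks by the factor (1 − b). Illustration with assumed post-randomization risks of 5% (usual care) and 10% (aerosol), a true ratio of 2.00:

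| b (assumed) | Usual care | Aerosol | Ratio | Difference, points |
|---|---|---|---|---|
| 0% | 5.0% | 10.0% | 2.00 | 5.0 |
| 2% | 6.9% | 11.8% | 1.71 | 4.9 |
| 5% | 9.75% | 14.5% | 1.49 | 4.75 |
| 10% | 14.5% | 19.0% | 1.31 | 4.5 |
| 20% | 24.0% | 28.0% | 1.17 | 4.0 |

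The ratio is sensitive to even a small b. The absolute difference is not, unless b is large.

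**The case against.** The strongest reply is that section 8.1 sets an extraction window, not a counting rule. Data from birth are needed to describe baseline, and section 9.1 defers detail to a SAP still to be developed, with data exclusions documented before database lock. This stands in part: the text never says that earlier events count as outcomes. But birth to day 28 is the only window attached to those incidences, and nothing later narrows it.

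Second, the sentence that starts at birth introduces only the second block of 8.1. A reader might infer that it also fixes the window for instillation effects, so that the birth instillation is a declared trial outcome. The documents do not support that. The instillation item is in the first block with no window, the form's age field allows the birth instillation to be removed, and delivery-room intubation and surfactant are already recorded with the demographic data. The Step 2 and Step 3 results therefore hold only on one reading, though nothing in the text rules it out.

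Third, the contrast with efficacy is incomplete. The primary, severity and section 4.1 lung-injury endpoints start at randomization. The duration endpoint in 4.1 has no stated start, section 7.2 item 3 runs from birth, and item 4 gives no start.

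Finally, no between-arm safety test or margin is planned, so no formal decision would be reversed. That is correct. The effect is on how the tables will be read.

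**Conclusion.** The gap is real and should be closed before database lock. As written, events before and after randomization can be mixed in the safety tables, and form items 6 and 7 cannot by themselves separate those close to randomization. Ratios and any-event proportions move toward no difference; differences in event counts are unchanged in expectation and only noisier.

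The largest effect that can be sized is in cohort 2: 66% of expected instillations would precede treatment, and a 30% relative reduction would appear as 11%. This is conditional on counting the birth instillation and on the plan's 60% and 42%, and the absolute difference stays at 18. For early hemorrhage, infection and other severe events the direction is clear, but the size rests on assumed values of b.

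A reader might go further and infer that every listed harm is diluted, or that the plan will conceal a harm. Neither follows: bronchopulmonary dysplasia cannot precede randomization, the main known brain injuries are excluded at entry, and the plan specifies tabulation rather than a safety conclusion rule.

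**What to change.** In section 8.1 and in the SAP:
- Start the comparative safety window at randomization.
- Limit the instillation item to instillations after randomization. In cohort 2, the age field in form item 5 identifies the qualifying one, given at or before 1 hour of age.
- Count events that are new after randomization or that worsen in grade or severity after it. Counting only first diagnoses would lose, for example, a low-grade hemorrhage that progresses.
- Show events before randomization separately, by arm, as baseline history.

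On the case report form, add a randomization date and time, which it lacks, and an onset date and time for each diagnosis in item 7.

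The cost is protocol and SAP wording, the added form fields, slightly smaller event counts, and some review of the progress notes for days 1 to 28, already uploaded, to order events on the first day. No treatment or clinical rule changes.

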9. STATISTICS

9.1 Statistical Methods

ONY, Inc., or its designee, will be responsible for (a) data management, (b) reviewing and validating all information in the clinical report forms, (c) statistical analysis, and (d) generation of the clinical study report. A Statistical Analysis Plan (SAP) providing details of statistical analyses performed after completion of the study will be developed. Prior to locking the database, all data editing will be completed and decisions regarding the evaluability of subject data for inclusion in statistical analyses will be made. The rationale for excluding any data from statistical analyses will be prospectively defined, and classification of all or part of a subject's data as non-evaluable will be documented before the database is locked and the statistical analysis is begun. ONY, Inc., or designee will perform the statistical analysis of the data derived from this study. All analyses will be carried out using SAS version 9.4 (or higher) statistical software (Cary, NC).

Statistical design: This study is a randomized, multiple-center clinical trial designed to assess the superiority of the experimental intervention (aerosolized Infasurf) relative to active control (“usual care”) with regards to the incidence of intubation and instillation of liquid surfactant suspension. A total of up to 200 subjects who received instillation of surfactant for RDS in the first hour of life (“the post-instilled cohort”) and up to 458 subjects who did not receive surfactant at birth who develop RDS in the first hours of life (“the uninstalled cohort”) will be enrolled. Treatment assessment will be done for each cohort separately, that is, this study may be thought of as two individual trials under one protocol.

Stratification: The randomization will be stratified by center and patient cohort and significance tests applied in the analyses will be stratified by center.

Randomization: Subjects will be randomized to the intervention or active control arm in a 1:1 fashion using a stratified permuted block randomization scheme with variable block sizes of 2 and 4. Randomization lists will be generated by the study biostatistician which will then be used to create an envelope-based system to be used at the individual study sites. Subjects will be included in primary data analyses according to their randomized assignment irrespective of the treatment actually received (intent-to-treat). Exceptions would include those who withdraw their consent to use any of their data prior to subject evaluation.

Accrual. Subjects will be accrued to the study on a first-come basis. The projected accrual is approximately 80 per month, and therefore recruitment is expected to be complete at most 365 days following the study starting point. Subjects will be followed to hospital discharge or 28 days whichever is shorter so total study duration will be approximately 13 months.

Descriptive analyses. Measured outcome variables will be summarized overall and by relevant demographic and baseline variables. Descriptive statistics such as frequencies and relative frequencies will be computed for all categorical variables. Numeric variables will be summarized using simple descriptive statistics such as the mean, standard deviation and range. A variety of graphical techniques will also be used to display data, ex. histograms, boxplots, scatterplots, etc.

Primary efficacy analyses. The primary efficacy analysis will be performed within each cohort separately and is based on a test for superiority of the experimental treatment relative to active control with regards to intubation rate. An overall assessment of the probability of intubation differences across study sites will be done using the Cochran-Mantel-Haenszel test. A one-sided nominal significance level of 5% will be utilized. Additional analyses will be performed utilizing both cohorts of subjects in order to assess differential treatment effects.

Primary safety analyses. All adverse events will be recorded during the study period and then tabulated at the end of the study.

Secondary analyses. Secondary efficacy outcomes representing measures of severity of RDS (oxygen supplementation and respiratory support measures from randomization to Surfactant Instillation or 72 hours of age, whichever comes first) will be summarized using standard descriptive statistics and compared between treatment groups using the stratified Wilcoxon rank sum test. In the case of outcomes measuring the duration of acute RDS (duration of supplemental oxygen), so to accommodate the potential censoring involved, distributional estimates will be based on the Kaplan-Meier method and groups differences statistically assessed using the stratified log-rank test. For the comparison of measures of protection from acute lung injury (incidence of lung air leaks or pulmonary hemorrhage from randomization to 72 hours or intubation and surfactant instillation), the Cochran-Mantel-Haenszel test will be used. All statistical tests will be one-sided and tested at a 5% nominal significance level.

Interim analysis. A group sequential approach will be utilized in the statistical evaluation of data, with a two interim analyses and the final analysis planned. The interim analyses, which will assist in making the decision of whether or not to stop the trial early for futility, will take place after the study outcome variables are observed in approximately the first 1/3 of evaluable subjects and after approximately 2/3 of evaluable subjects. Assuming increasing recruitment during the months and allowing for data clean up and statistical analysis, we anticipate the interim analysis will be performed at approximately 4 months after enrollment of the first patient. The principal interim analyses will involve the computation of the conditional power pertaining to the test of the primary efficacy outcome, that is, we will compute the probability of rejecting the primary null hypothesis at the end of study given the data observed thus far. In the event of unfavorable trends in the data, the conditional power of achieving a final conclusion of superiority will be much less than the initial planned power of the study for a given point in the alternative parameter space, thus making conditional power a quantitative tool for use in interim decision making. Monte Carlo simulations based on 10,000 iterations will be utilized to compute the conditional power under two difference scenarios: 1) assuming the parameter values utilized for sample size derivation, and 2) assuming the true parameter values are equal to the sample estimates computed from the interim data. Given the uncertainty in the actual values of the parameters, the conditional power associated with the second scenario should be viewed as that which is most informative in decision making. Additionally, 95% confidence intervals will be obtained and used to assess if the values assumed in the planning of the study are much different than those suggested by the data. The conditional power for selected values within the computed confidence intervals may be calculated if deemed potentially informative. Results of interim analyses will be reviewed by the Data and Safety Monitoring Board. After the second interim analysis, sample size may be modified using the method discussed in Gould (1992),⁷ performed in conjunction with an effect size of a 20% decrease in intubation rate.

